 - c. Proinflammatory cytokine profile (IL-17 and IFN γ) [baseline, 4 weeks, and 6 months]

The most extensively studied surrogate endpoint in PSC is serum alkaline phosphatase (ALP). Our group at Mayo Clinic and others have reported an association between serum ALP and clinical outcomes in PSC. Specifically, normalization of serum ALP appears to be associated with long-term survival free of CCA, liver transplantation, liver-related death, and colorectal cancer and persistent ALP elevation has been associated with worse outcomes in PSC.⁵⁹⁻⁶¹ Therefore, we have chosen this simple, rapid, inexpensive, and minimally invasive test as our primary endpoint. AST, ALT, and bilirubin will be monitored to assess general liver health during the treatment. AST, ALT, or total bilirubin elevation can signal increased liver damage or liver cell necrosis, while elevated direct bilirubin may indicate bile duct obstruction. Further, it is hypothesized that treatment with VC will result in a reduction of IL-17 and IFN γ production. Levels of these cytokines will be measured at 4 weeks and at 6 months (end of study) and compared to baseline. The early 4-week time point will be used to determine whether early changes in these cytokines may predict improvements in ALP.

A 25% improvement in ALP with no more than a 33% worsening of AST after 6 months of treatment will be assessed as a positive outcome. While full normalization of ALP levels is unlikely over the short course of this pilot study, a 25% improvement would be deemed significant, indicating that VC has a positive effect on the progression of PSC. A less than 33% increase in AST levels concomitant with this ALP reduction would be acceptable, as it would be considered only a mild elevation. While a recent consensus statement from the International PSC Study Group indicates that transient elastography (TE), a new technique that allows non- invasive assessment of liver fibrosis, is one of the top three most promising surrogate endpoints for PSC (along with ALP and liver histology),⁶² it is unlikely that significant changes in TE would manifest in the 6-month course of this study. Thus, TE will not be included as an endpoint. Reduction of proinflammatory cytokines IL- 17 and IFN γ at the early 4-week time point concomitant with reduced ALP at the end of study would indicate a role for cytokine levels as an early predictor of improvements.

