A 25% improvement in ALP with no more than a 33% worsening of AST after 6 months of treatment will be assessed as a positive outcome. While full normalization of ALP levels is unlikely over the short course of this pilot study, a 25% improvement would be deemed significant, indicating that VC has a positive effect on the progression of PSC. A less than 33% increase in AST levels would be considered only a mild elevation and as such would be tolerable when accompanied by a concomitant reduction of ALP. While a recent consensus statement from the International PSC Study Group indicates that transient elastography (TE), a new technique that allows non-invasive assessment of liver fibrosis, is one of the top three most promising surrogate endpoints for PSC (along with ALP and liver histology), it is unlikely that significant changes in TE would manifest in the 6 month course of this study. Thus, TE will not be included as an endpoint.

Vidofludimus calcium will be supplied by Immunic AG, Munich, Germany throughout the full course of the clinical trial. It has been confirmed through consultation with NIDDK personnel that this is permissible under this funding opportunity and does not constitute undue involvement by a foreign component. As this is a single- arm pilot trial, no placebo will be used. All study medication will be manufactured, tested, and released according to current Good Manufacturing Practice guidelines and local requirements. The active ingredient is vidofludimus calcium. Inactive ingredients are microcrystalline cellulose EP, polyvidon K25, crospovidone EP type A, talc, and magnesium stearate. The tablet formulation consists of a specific polymorph of vidofludimus calcium. Tablets are white, uncoated, biconvex tablets with a diameter of 8 mm. The dosage strength will be 15 mg VC per tablet. Subjects will take one tablet once daily during lead-in dosing period and two tablets, once daily during the treatment period. A licensed pharmacist (designated by the co-investigator) at each research site's

pharmacy will be responsible for dispensing study medication. All study drugs will be labeled with "Caution: New Drug--Limited by Federal (or United States) law to investigational use" per 21 CFR 312.6.

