- Elevated total bilirubin $\geq 2 \times$ baseline that does not return to within 10% of baseline within two weeks
- Serious allergic reaction
- Pregnancy or breastfeeding

Non-adherence to the study protocol by a study subject may, at the discretion of the principal investigator, be grounds for termination.

Statistical Analysis Plan: The proportion of patients with normalization of serum ALP at 3 months and 6 months and their corresponding confidence intervals will be estimated using exact binomial method. The primary endpoint is ALP normalization (within the normal limits of the laboratory test) rate at 6 months. We will define success as a 95% CI that does not overlap 0 at 6 months. Further, we will further investigate if the absolute ALP decreases over time using mixed model with repeated measures to account for within patient correlation over time.

All the liver biochemistries and proinflammatory cytokine profile over time will be analyzed using mixed model with repeated measures to investigate how VC treatment plays a role over the 6 months duration. The liver biochemistries and proinflammatory cytokine will be dichotomized into abnormal and normal groups if possible and further the abnormal proportions at different time points will be estimated to see the trend over time.

The incidence, type and relatedness of serious adverse events and adverse events will be monitored and reported for all the subjects.

Adherence to Regulatory Standards: The investigators will ensure that this study is conducted in full conformity with Regulations for the Protection of Human Subjects of Research codified in 45 CFR Part 46, 21 CFR Part 50, 21 CFR part 56, and the ICH; Good Clinical Practice E6.

ClinicalTrials.gov Requirements: The principal investigator will ensure that this clinical trial is properly registered at www.clinicaltrials.gov, per the Public Law 110-85 (also known as the FDA Amendments Act (FDAAA) of 2007), no later than 21 days after the first subject is enrolled. The principal investigator will also ensure that the results (including adverse events) of this clinical trial are reported no later than 1 year after completion of the clinical trial.

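### The SAP judges success by ALP normalization at 6 months, while the protocol body calls a 25% ALP fall with a limited AST rise the positive outcome; the two are not reconciled, and the SAP does not apply the second

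*Combined protocol and SAP*

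**What the plan says.** **Statistical Analysis Plan** (within the Data and Safety Monitoring Plan). The endpoint is "The primary endpoint is ALP normalization (within the normal limits of the laboratory test) rate at 6 months", estimated with an exact binomial interval. The only success rule is "We will define success as a 95% CI that does not overlap 0 at 6 months". As an additional analysis, "we will further investigate if the absolute ALP decreases over time using mixed model with repeated measures". The liver biochemistries, which include AST, are also modelled over time, and "The liver biochemistries and proinflammatory cytokine will be dichotomized into abnormal and normal groups if possible".

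**Study Design and Methodology**, repeated in **Protection of Human Subjects, I(a)**. The criterion is "A 25% improvement in ALP with no more than a 33% worsening of AST after 6 months of treatment". The second half of that sentence gives its status: "no more than a 33% worsening of AST after 6 months of treatment will be assessed as a positive outcome". Both sections then say of the SAP's endpoint: "While full normalization of ALP levels is unlikely over the short course of this pilot study". They add that a 25% improvement would count as significant. The AST limit is restated in slightly different terms: "A less than 33% increase in AST levels concomitant with this ALP reduction would be acceptable".

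**Endpoint list** (Study Design and Methodology). The primary endpoint is improvement of ALP, with no threshold.

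**Inclusion Criterion b** requires baseline ALP of at least 1.5 x ULN. Planned enrolment is 30; Risk Mitigation and Alternative Strategies allows as few as 20.

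**The concern.** A reader of the protocol body would expect the trial to be judged on the 25% ALP / 33% AST outcome. A reader of the SAP would expect normalization. No section ranks one above the other or says how they relate, and the SAP judges the trial by an event that the protocol body twice calls unlikely.

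The SAP never names the 25% threshold, the 33% AST limit or their combination, and AST plays no part in success. The 25%/33% outcome is itself incomplete: it does not say whether it applies to each subject or to the group, or how many responders would be enough.

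With two unreconciled descriptions of a good result, the more favourable one can be chosen after the data are seen. The study is a small exploratory pilot, which limits the harm. Even so, under Importance of the Knowledge to be Gained it is meant to contribute to the judgement on whether larger studies are justified.

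**Working it through.** The documents give no sample-size calculation and no expected response rate, so there is no stated figure to reproduce. The check compares the two criteria.

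**Inputs.** Entry ALP of at least 1.5 x ULN (Inclusion Criterion b); n = 30, minimum 20; exact binomial 95% CI, computed as two-sided Clopper-Pearson; thresholds of 25% and 33% (Study Design and Methodology). The same ULN is assumed at both visits.

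**Step 1: fall needed to normalize.** With baseline b in multiples of ULN, the required fall is 1 - 1/b, and a 25% fall leaves 0.75 x b.

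| Baseline (x ULN) | Fall needed to normalize | Level after a 25% fall (x ULN) |
|---|---|---|
| 1.5 | 1 - 1/1.5 = 33.3% | 1.125 |
| 2 | 1 - 1/2 = 50% | 1.5 |
| 3 | 1 - 1/3 = 66.7% | 2.25 |

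A 25% fall normalizes only from a baseline of 1/0.75 = 1.33 x ULN or less, which is below the entry limit. No eligible subject normalizes with exactly a 25% fall.

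**Step 2: where the criteria can differ, read per subject.** A subject who normalizes from 1.5 x ULN or more has a month-6/baseline ratio of at most 1/1.5 = 0.667, below 0.75, and so always meets the ALP part. Two kinds of disagreement remain:

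- ALP falls by at least 25% but stays above normal, with AST within the limit: positive in the protocol body, not a SAP responder.
- ALP normalizes but AST rises by more than 33%: a SAP responder, not positive in the protocol body.

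**Step 3: the SAP rule in limiting cases.** For 0/n the lower limit is 0 and the upper limit is 1 - 0.025^(1/n). For 1/n the lower limit is 1 - 0.975^(1/n), which is above 0, so one normalizer meets the rule.

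| Case | Meet 25%/33% | Normalized | Exact 95% CI | SAP verdict |
|---|---|---|---|---|
| All fall exactly 25%, AST within limit, n = 30 | 30/30 | 0/30 | 0 to 11.6% | fails |
| Same, n = 20 | 20/20 | 0/20 | 0 to 16.8% | fails |
| One normalizes with AST up more than 33%, no other reaches a 25% fall, n = 30 | 0/30 | 1/30 | 0.08% to 17.2% | succeeds |
| Same, n = 20 | 0/20 | 1/20 | 0.13% to 24.9% | succeeds |

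**Step 4: what the other planned analyses would show.** In the first case every month-6 value is 0.75 x baseline, so the mean also falls by 25% and the mixed model of absolute ALP would show it. The AST model would likewise show the average AST change. Neither model counts subjects who meet both limits, and splitting results into normal and abnormal uses different cut-points.

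**The case against.** The strongest reply is that the SAP alone supplies a complete success rule and therefore governs, with the 25%/33% statement as clinical context. Normalization also has a stated rationale: the protocol cites its association with long-term survival free of major complications. And this is an exploratory pilot. The rationale and the pilot status stand. The claim that the SAP governs does not, because no section says so, and the 25%/33% statement carries thresholds, a timepoint and a commitment on how the result will be assessed.

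Four stronger readings are tempting, and the documents do not support them:

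- **That no planned analysis would reveal a 25% effect.** The mixed models of ALP and AST would show average changes. Only the thresholds and the combined outcome are missing.
- **That the plan will return a verdict opposite to the protocol's own.** The protocol body gives no trial-level rule for the 25%/33% outcome and does not list it as an endpoint. The supportable statement is that the criteria can disagree. The limiting cases are extreme, and how often disagreement would occur depends on baseline ALP, measurement noise and spread of response, none of which the documents give.
- **That the endpoint list contradicts the SAP.** Improvement without a threshold neither contradicts normalization nor settles the question.
- **That this trial's result alone decides on larger studies.** The protocol says only that it will help in that judgement.

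The two wordings of the AST limit differ only at exactly 33%, so that is a matter of tidying.

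**Conclusion.** The point holds. The SAP's primary endpoint and only success rule rest on normalization, the protocol body names a different outcome as positive, and nothing reconciles them. Normalization requires a fall of at least 33.3% in every eligible subject and 50% from 2 x ULN, against the 25% that the protocol body treats as significant. The AST condition has no counterpart in the SAP's rule.

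The conflict in the text rests on no assumption. The arithmetic assumes one ULN across visits, and the limiting cases also assume a per-subject reading with every subject evaluable. No claim is made about how likely disagreement is. Because it concerns the primary criterion, it should be settled before outcome data are examined.

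**What to change.** Amend Study Design and Methodology, Protection of Human Subjects I(a) and the Statistical Analysis Plan to give one primary endpoint and one success rule, and align the endpoint list with them.

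- **Smallest repair.** Keep normalization at month 6 as primary, with the success rule unchanged, and say so in both protocol-body sections. Add the 25%/33% outcome to the SAP as a named secondary analysis: the proportion of subjects at month 6 with ALP at or below 0.75 x baseline and AST within the 33% limit, with an exact 95% CI.
- **Alternative.** Make the 25%/33% outcome primary, with its own stated per-subject success rule, and keep normalization as secondary. The sponsor would have to supply that rule, since the documents do not contain one.

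In either case, word the AST limit one way throughout, and report ALP percent change from baseline at months 3 and 6 beside the mixed model of absolute ALP.

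**Cost.** No new data are needed, because ALP and AST are already measured at baseline, 3 and 6 months. The smallest repair adds one responder analysis and a percent-change summary. Either option needs a protocol amendment with IRB review and approval before it takes effect, as Recruitment and Informed Consent requires.

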Vidofludimus is a **potent inhibitor of human DHODH**, three times more effective than teriflunomide. A second important and distinguishing property of vidofludimus is its **potent inhibition of IL-17 and IFN γ release** from stimulated immune cells. Inhibition of IL-17 production was found to be independent of its effects on lymphocyte proliferation and it is believed that both these independent activities of vidofludimus contribute to its therapeutic effects in IBD.^{50,58} This **dual mechanism of action** confers a unique advantage over other DHODH inhibitors and makes vidofludimus a promising therapeutic option for both UC and PSC, diseases with frequent comorbidity and a common pattern of Th17 lymphocytic infiltration. With good clinical data for UC already in hand and a more comprehensive UC study in the works, a pilot trial for PSC is warranted. Success would result in a major step towards an effective

treatment for PSC where one does not currently exist.

Approach

We are proposing to test the hypothesis that vidofludimus calcium, a novel drug product, will be an effective treatment strategy for the rare but devastating disease primary sclerosing cholangitis. The rationale for this is based on **i) the strong linkage between ulcerative colitis and PSC; ii) the known involvement of Th17 lymphocytes and IL-17 in both disorders; iii) the demonstrated effect of vidofludimus on lymphocyte proliferation and IL-17 production; and iv) clinical evidence for the efficacy of vidofludimus in patients with UC.** Our approach is to investigate this hypothesis using a small two- center pilot study employing serum alkaline phosphatase, a surrogate marker having a well-established association with clinical outcome, as our primary endpoint. We further hypothesize that treatment with VC will affect profiles of proinflammatory cytokines and will assess IL-17 and IFNy levels as a potential early indicator of improvements in ALP.

The Specific Aims of the study are:

1. Determine if VC reduces serum alkaline phosphatase (ALP) in adults with PSC. Levels of serum ALP after 3 and 6 months of VC treatment will be compared with baseline (month 0).
2. Assess other liver biochemistries (an indication of general liver health) at 3 and 6 months of VC treatment and compare to baseline (month 0).
3. Determine if changes in the proinflammatory cytokines IL-17 and IFNy predict response to VC. Cytokines will be measured at baseline, 4 weeks, and 6months.

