These results will help us:

- Establish feasibility of the hypothesis that VC will play a therapeutic role in treatment of PSC
- Gain insight into the effect of VC on profiles of the proinflammatory cytokines IL-17 and IFNy
- Pave the way for more comprehensive clinical studies

Study Design and Methodology

This pilot study will be a 6-month, 30-subject clinical trial to assess the effects of VC on a surrogate biochemical endpoint known to have relevant association with clinical outcomes in PSC. All endpoint tests chosen are rapid, inexpensive, and minimally invasive. Due to the low prevalence of PSC, the study will be a single-arm, open-label study. The study will be undertaken at two sites, Mayo Clinic, Rochester, Minnesota (20 subjects) and Mayo Clinic, Phoenix, Arizona (10 subjects), both of which are tertiary referral centers for PSC. Immunic AG, a biotechnology company based in Munich, Germany, will supply the study agent in sufficient quantities for the study (see Letter of Support from Immunic AG). We have confirmed through consultation with NIH personnel that this is permissible under this funding opportunity.

During the 6-month treatment period, subjects will receive 30 mg VC orally once daily, a dose determined to be both safe and therapeutically relevant based on previous clinical studies (see Table 1). This will be preceded by a lead-in dosing period where subjects will receive 15 mg VC once daily for 1 week. Lead-in dosing is used to minimize the risk of drug intolerance during the initial treatment period. While no clinically relevant adverse events have been noted at 30 mg once daily dosing, in rare instances potentially drug-related hematuria has been observed in the first few days of treatment at higher doses (≥ 70 mg/day). As a precaution, subjects will be monitored for two weeks after initial drug

exposure for elevated erythrocytes in the urine by a dipstick test. It is not anticipated that hematuria will be seen if it has not developed within the first two weeks of drug exposure.

The following endpoints will be assessed at various times during the study and compared with baseline:

- i. Primary endpoint:
 - a. Improvement of serum alkaline phosphatase (ALP) [baseline, 3 months, and 6 months]
- ii. Secondary endpoints:
 - a. Bilirubin, Total and Direct [baseline, 3 months and 6months]
 - b. AST and ALT (aspartate and alanine transaminases) [baseline, 3 months, and 6 months]

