Due to the relatively low prevalence, it is possible that 30 subjects meeting inclusion criteria cannot be recruited within the planned 6-month recruitment period or that they are not split roughly equally between the two sites. In that case, we will extend the recruitment period and if required, we will execute the study with as few as 20 subjects, regardless of the distribution between sites. After the study is complete, further research may reveal other potentially interesting biomarkers that should be examined and thus we have included storage of extra blood draws during the study. Given the pilot nature of this study, it is possible that benefits are seen even though results are not conclusive. Study data may be examined more carefully to determine if benefits occur in a distinct subpopulation of subjects (e.g. in PSC patients with UC versus those without).

Overall, considering the known safety data, the implemented risk minimization measures, the expected benefits in the target population, and the unmet medical need for treatment in PSC, the risk-benefit evaluation is considered favorable.

PROTECTION OF HUMAN SUBJECTS

This Human Subjects Research meets the definition of a clinical trial.

I. Risks to Human Subjects

a) Human Subjects Involvement, Characteristics, and Design: A total of 30 adults (age range 18-75 years) who meet the criteria for diagnosis of primary sclerosing cholangitis (PSC), as defined by the American Association for the Study of Liver Diseases (AASLD) published guidelines, will be enrolled into this study from two centers. PSC patients with and without inflammatory bowel disease (IBD) will be included. Other inclusion and exclusion criteria are detailed below:

Inclusion Criteria

- a. Male or female subject age 18-75 years
- b. Diagnosis of PSC consistent with the guidelines published by the AASLD. All subjects must have an elevated serum ALP of at least 1.5 times upper limit of normal (ULN) at baseline plus cholangiographic evidence of PSC (MRI, endoscopic retrograde cholangiography, or direct cholangiography).
- c. Indirect bilirubin <1.2 times the ULN
- d. An ultrasound (or equivalent imaging modality) that excludes biliary obstruction and malignancy within 6 months of study enrollment
- e. PSC with or without inflammatory bowel disease, such as ulcerative colitis or Crohn's disease
- f. Must agree to comply with the study protocol and provide informed consent

Exclusion Criteria

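### The primary endpoint is ALP normalization, a cut the plan does not expect subjects to reach, while Aim 1 and the 25% target concern ALP change; the success rule has little error control, and the power lost at equal error may be large but depends on unstated inputs

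*Combined protocol and SAP*

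**What the plan says.** The Statistical Analysis Plan paragraph (Data and Safety Monitoring Plan) fixes the primary endpoint: "The primary endpoint is ALP normalization (within the normal limits of the laboratory test) rate at 6 months". It adds that "their corresponding confidence intervals will be estimated using exact binomial method" and sets the success rule: "We will define success as a 95% CI that does not overlap 0 at 6 months". A repeated-measures mixed model of absolute ALP is planned as a further analysis, without a success criterion.

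Other sections describe a different target. Specific Aim 1 asks whether the drug reduces ALP: "Levels of serum ALP after 3 and 6 months of VC treatment will be compared with baseline (month 0". Study Design and Methodology lists the primary endpoint as "Improvement of serum alkaline phosphatase (ALP) [baseline, 3 months, and 6 months". The same section, repeated in Protection of Human Subjects I.a, says: "While full normalization of ALP levels is unlikely over the short course of this pilot study, a 25% improvement would be deemed significant". There a positive outcome is a 25% ALP improvement with AST worsening limited to 33%.

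Inclusion criterion b sets the floor: "All subjects must have an elevated serum ALP of at least 1.5 times upper limit of normal (ULN) at baseline". The planned size is 30, and Risk Mitigation and Alternative Strategies allows as few as 20.

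**The concern.** The primary analysis reduces each subject's ALP course to normal or not normal at month 6. The cut lies beyond the effect the plan calls meaningful, and the plan itself doubts it will be reached. It also ignores the subject's own baseline: a fall from 4 to 1.1 x ULN counts the same as no change.

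Two things are at stake. The primary result may rest on a few subjects who started near 1.5 x ULN and so fail to answer Aim 1. And the success rule may be met by one fluctuating value, so a declared success would say little about the drug. This study is meant to decide whether larger trials are justified, so both errors matter.

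**Working it through.** **What follows from the documents alone.** A 25% fall from the entry floor gives 1.5 x 0.75 = 1.125 x ULN, still abnormal. The fall needed to reach 1.0 x ULN from baseline B is 1 - 1/B: 33.3% from 1.5, 50% from 2.0, 60% from 2.5.

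**The success rule.** The exact lower 95% limit for one event in n is 1 - 0.975^(1/n): 0.08% for 1/30 and 0.13% for 1/20. Both exceed 0, so the rule amounts to at least one normalizer. Its success probability at rate p is 1 - (1 - p)^n. At n=30 that is 45.5% for p = 2%, 78.5% for 5% and 95.8% for 10%.

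**Power at equal error.** The documents contain no power calculation, ALP SD, baseline distribution or untreated normalization rate, so there is no plan figure to reproduce. Assumptions:
- Baseline ALP in x ULN is lognormal, truncated at 1.5 (pre-truncation median/log-SD 1.8/0.4, 2.2/0.5, 2.5/0.5; medians after truncation about 2.1, 2.5, 2.8).
- The SD of within-subject log change is 0.2 to 0.4.
- The drug lowers ALP by 25% on average in everyone, with no dropout and no drift without drug.

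Formulas:
- p0 and p1 are the simulated month-6 normalization rates without and with the effect.
- The normalization test uses the smallest r with P(X >= r | n, p0) <= 2.5%; its power is P(X >= r | n, p1).
- The paired log-ALP test (two-sided 5%) uses the noncentral t with noncentrality sqrt(n) x ln(1/0.75)/SD. For n=30 and SD 0.3 this is 5.477 x 0.2877/0.3 = 5.25.

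Results at n=30:

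| Median | SD | p0 | p1 | Written rule, no effect | Written rule, 25% fall | r | Normalization power | Paired power | Loss (points) |
|---|---|---|---|---|---|---|---|---|---|
| 2.1 | 0.2 | 0.2% | 4.8% | 6% | 77% | 2 | 43% | >99.9% | 57 |
| 2.1 | 0.3 | 1.7% | 9.7% | 40% | 95% | 3 | 57% | 99.9% | 43 |
| 2.1 | 0.4 | 4.45% | 14.4% | 74% | 99% | 5 | 44% | 97% | 53 |
| 2.5 | 0.2 | 0.1% | 3.0% | 4% | 60% | 2 | 23% | >99.9% | 77 |
| 2.5 | 0.3 | 1.1% | 6.3% | 28% | 86% | 3 | 29% | 99.9% | 71 |
| 2.5 | 0.4 | 3.0% | 9.8% | 59% | 96% | 4 | 34% | 97% | 63 |
| 2.8 | 0.2 | 0.1% | 2.3% | 3% | 51% | 2 | 15% | >99.9% | 85 |
| 2.8 | 0.3 | 0.8% | 5.0% | 22% | 79% | 3 | 19% | 99.9% | 81 |
| 2.8 | 0.4 | 2.4% | 8.1% | 51% | 92% | 4 | 22% | 97% | 75 |

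**Wider assumptions.** With an exponential tail on the log scale above 1.5 x ULN (median 1.75 to 3.0) and SD 0.15 to 0.80, the loss is 15 to 76 points at n=30 and 12 to 87 at n=20. With a median of 1.75 and n=30 it is only 15 to 43.

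**A responding subset.** If 20% to 50% of patients fall by 40% to 70% and the rest do not respond, the loss runs from -25 to +40 points at n=30 and -41 to +45 at n=20. Example: 20% fall by 70%, SD 0.2, median 2.0. Then p0 = 0.3%, p1 = 16.9%, r = 2, and normalization power is 97% against 73% for the paired test.

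**A 25% responder rate.** Ignoring the AST condition, p0 = Phi(ln 0.75/SD) and p1 = 50%. At n=30 and SD 0.2, 0.3, 0.4, power is over 99%, 98% and 82%, a loss of 0 to 15 points against the paired test (up to 27 at n=20).

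**The case against.** - **The written rule is not short of power.** A reader might infer from the equal-error comparison that the planned analysis would miss a 25% fall. The documents do not support that. They contain no test against a non-zero rate, and the rule as written succeeds in 51% to 99% of trials in the table. Its main fault is error control; the power loss appears once that is repaired. If a null rate of exactly zero is taken literally, one normalizer does refute it, but the documents give no reason to think spontaneous normalization never occurs.
- **No fixed loss can be claimed.** A reader of the table might infer a minimum of 40 points. That holds only within its assumptions. The wider grid reaches 15 at n=30, and the sign can reverse with a strongly responding subset. The plan allows for subgroup benefit under Risk Mitigation and Alternative Strategies, although its stated target is a 25% improvement.
- **The loss does not extend to every responder definition.** It comes from where the normalization cut sits; the plan's own 25% threshold costs far less.
- **The paired analysis has its own weakness.** Subjects are selected on high ALP, and screening values may serve as baseline (Timeline and Schedule; Table 3, footnote a). If all the log-change SD is visit-to-visit noise, a strong assumption, ALP falls 1% to 10% without drug and the paired test succeeds in 5% to 32% of trials at n=30, against a nominal 2.5%. Selection would also affect the normalization null. The power comparison models drift on neither side.
- **Zero is a lower bar than 25%.** At n=30 and SD 0.2 to 0.4, an interval below 0% needs an observed fall of only 1 - exp(-2.045 x SD/sqrt(30)), or 7% to 14%.
- **Part of the answer is already planned.** The mixed model analyses ALP change, the trial is exploratory, and normalization has a cited association with outcome. This stands, and limits the severity.

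**Conclusion.** The mismatch is established by the documents: the primary endpoint is a cut the plan calls unlikely to be reached, it does not match Aim 1 or the listed primary endpoint, and a fall of exactly 25% always scores as failure. That one normalizer meets the success rule is also exact.

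The sizes are conditional. The no-effect success rate of about 3% to 74% at n=30 rests on the assumed baselines and SD 0.2 to 0.4. The equal-error loss of roughly 15 to 75 points at n=30, up to about 85 in some scenarios, also rests on a uniform 25% fall and no drift without drug. The defect should be corrected before analysis, but it does not invalidate the data, since the ALP values needed are already scheduled.

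**What to change.** In the Statistical Analysis Plan, make the primary analysis the within-subject change in log ALP from baseline to month 6. Estimate it from the repeated-measures model already planned, put on the log scale, and report a geometric mean percentage change with 95% CI. Require the CI to lie entirely below 0%, and report the estimate and interval against the plan's own 25% mark. Keep normalization rates at months 3 and 6, with exact CIs, as descriptive secondaries.

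Reconcile Study Design and Methodology, Protection of Human Subjects I.a and the Statistical Analysis Plan so that they name one primary endpoint. State that the result is an uncontrolled before-after change that may include regression to the mean, because subjects are selected on high ALP and screening values may serve as baseline.

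The cost is revised wording and an updated primary endpoint, with no new visits, samples or patients. The small downside is that mean change is less directly tied than normalization to the outcome associations the protocol cites, which is why normalization stays in the report.
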